7.2.1.1. Metabolic Assessments

For the lipid panel and glucose measurements, only those under fasting status will be summarized for subjects in the Safety Analysis Set from baseline to Week 96. P-values for the difference between the 2 treatment groups in baseline values and the change from baseline in fasting lipid and glucose data (including total cholesterol, triglycerides, LDL, HDL, total cholesterol to HDL ratio, and glucose) will be estimated from the 2-sided Wilcoxon rank sum test.

Fasting lipid data (including total cholesterol, LDL, HDL and triglycerides) will also be analyzed using the following National Cholesterol Education Program (NCEP) Adult Treatment Panel (ATP) III categories {National Cholesterol Education Program (NCEP) 2001}:

- For total cholesterol (mg/dL): < 200 (desirable), 200-239 (borderline high), and ≥ 240 (high)
- For LDL (mg/dL): < 100 (optimal), 100-129 (near optimal/above optimal), 130-159 (borderline high), 160-189 (high), and ≥ 190 (very high)
- For HDL (mg/dL): < 40 (low), 40-59 (normal), and ≥ 60 (high)
- For triglycerides (mg/dL): < 150 (normal), 150-199 (borderline high), 200-499 (high), and ≥ 500 (very high)

The number and proportion of subjects for the above categories of each lipid parameter will be summarized by its baseline category for each treatment group at each visit.

The summaries described above will be repeated for the subjects in the Open-Label Safety Analysis from open-label baseline to Week 96 using open-label baseline instead of baseline, and no statistical comparisons will be made.

7.2.1.2. Calcium Corrected for Albumin

Calcium corrected for albumin will be calculated and summarized by-visit for subjects in the Safety Analysis Set from baseline to Week 96, and separately for subjects in the Open-Label Analysis Set from open-label baseline to Week 96. The following formula will be used when both serum calcium and albumin results for a given blood draw are available and serum albumin value is < 4.0 g/dL.

Calcium corrected for albumin (mg/dL) serum calcium (mg/dL) $+ 0.8 \times (4.0 \text{ albumin (g/dL)})$

When albumin value is ≥ 4.0 g/dL, the actual calcium results will be used. Toxicity grading for calcium will be applied based on the corrected values.

7.2.2. Graded Laboratory Values

The criteria specified in the protocol will be used to grade laboratory results as Grade 0, Grade 1 (mild), Grade 2 (moderate), Grade 3 (severe) or Grade 4 (life-threatening). Grade 0 includes all values that do not meet criteria for an abnormality of at least Grade 1. Some laboratory tests have criteria for both increased and decreased levels; analysis for each direction (ie, increased, decreased) will be presented separately.

For triglycerides, LDL, and total cholesterol, the protocol-specified toxicity grade scale is for fasting test values; non-fasting lipid results (or lipid results without known fasting status) will not be graded or summarized by toxicity grades.

7.2.2.1. Treatment-Emergent Laboratory Abnormalities

Treatment-emergent laboratory abnormalities occurring in the double-blind phase are defined as values that increase by at least 1 toxicity grade from baseline at any postbaseline visit up to and including the minimum of the blinded study drug stop date + 3 days and the first dose date of open-label study drug, if applicable, for those who discontinued blinded study drug permanently, or values that increase by at least 1 toxicity grade from baseline at any postbaseline visit for those who are still on double-blind study drug. If the relevant baseline laboratory value is missing, any laboratory abnormality of at least Grade 1 observed within the double-blind phase will be considered treatment emergent.

Treatment-emergent laboratory abnormalities occurring in the open-label phase are defined as values that increase by at least 1 toxicity grade from open-label baseline at any open-label postbaseline visit up to and including the last dose date of the open-label study drug + 3 days for those who discontinued open-label study drug permanently, or values that increase by at least 1 toxicity grade from open-label baseline at any open-label postbaseline visit for those who are still on open-label study drug. For the analyses of abnormalities occurring during open-label treatment, open-label baseline will be the last available record on or prior to Open-Label Study Day 1.

Post-treatment-emergent laboratory abnormalities occurring in the TFFU phase are defined as values that increase by at least 1 toxicity grade from TFFU baseline. For the analyses of abnormalities occurring during the TFFU phase, TFFU baseline will be the last available record on or prior to last dose date + 3 days.

Fasting glucose and nonfasting glucose (including glucose results without a known fasting status) are graded based on different grading scales as specified in the protocol. Treatment-emergent and post-treatment-emergent laboratory abnormalities will be summarized for fasting glucose. Since nonfasting glucose was not assessed at baseline, the maximum postbaseline grade will be summarized.

7.2.2.2. Treatment-Emergent Marked Laboratory Abnormalities

Treatment-emergent marked laboratory abnormalities occurring in the double-blind phase are defined as values that worsen by at least 3 grades from baseline at any postbaseline visit up to and including the minimum of the blinded study drug stop date + 3 days and the first dose date of open-label study drug, if applicable, for those who discontinued blinded study drug permanently, or values that worsen by at least 3 grades from baseline at any postbaseline visit for those who are still on blinded study drug. If relevant baseline laboratory data are missing, any laboratory abnormalities of at least Grade 3 or 4 observed within the double-blind time frame specified above will be considered as treatment-emergent marked laboratory abnormalities during the double-blind phase.

Treatment-emergent marked laboratory abnormalities occurring in the open-label phase are defined as values that worsen by at least 3 grades from open-label baseline at any open-label postbaseline visit up to and including the date of last dose of open-label study drug + 3 days for those who discontinued open-label study drug permanently, or values that worsen by at least

3 grades from open-label baseline at any open-label postbaseline visit for those who are still on open-label study drug.

Post-treatment-emergent marked laboratory abnormalities will not be summarized for the TFFU phase.

7.2.2.3. Summaries of Laboratory Abnormalities

The following summaries (number and percentage of subjects) of laboratory abnormalities will be provided by treatment group (subjects categorized according to most severe abnormality grade) for (1) subjects in the Safety Analysis Set during the double-blind phase, (2) subjects in the Open-Label Safety Analysis Set during the open-label phase, and (3) subjects in the TFFU Safety Analysis Set during the TFFU phase:

- Treatment-emergent laboratory abnormalities
- Treatment-emergent Grade 3 and 4 laboratory abnormalities
- Treatment-emergent marked laboratory abnormalities (this will not be summarized for (3))

For all summaries of laboratory abnormalities, the denominator is the number of subjects with any nonmissing postbaseline (or open-label postbaseline, or post-TFFU baseline) value in the given study period. By-subject listings of Grade 3 or 4 and graded laboratory abnormalities will be provided by subject ID number and visit in chronological order.

7.2.3. **ALT Elevation**

An ALT elevation is defined as serum ALT $> 2 \times$ open-label baseline value and $> 10 \times$ ULN, with or without associated symptoms. Confirmed ALT elevation (ALT flare) is defined as ALT elevations at 2 consecutive open-label postbaseline visits. All treatment-emergent ALT elevations including confirmed ALT elevations will be summarized for the open-label phase only. All treatment-emergent and nontreatment-emergent ALT elevations will be included in a listing.

7.3. Bone Safety Analyses

7.3.1. Bone Mineral Density (BMD)

Percentage change from baseline in hip BMD and spine BMD during the entire study treatment period will be summarized by treatment group and visit using descriptive statistics for subjects in the Hip and Spine DXA Analysis Sets. Percentage change from open-label baseline in hip BMD and spine BMD during the open-label phase will be summarized by treatment group and visit using descriptive statistics for subjects in the Open-Label Hip and Spine DXA Analysis Sets.

For each subject and visit, the clinical BMD status will be defined for hip and spine BMD based on the corrected t-score in Table 7-1.

Clinical Status	BMD T-Score
Normal	t-score ≥ -1.0
Osteopenia	-2.5 ≤ t-score < -1.0
Osteoporosis	t-score < -2.5

Table 7-1. Normal, Osteopenia, and Osteoporosis as Defined by T-Score

The number and percentage of subjects in each clinical BMD status (normal, osteopenia, and osteoporosis) will be summarized by visit and by baseline (or open-label baseline) clinical status for both hip and spine using observed data. Only for the entire study treatment period summary, the distribution of the clinical BMD status will be compared between the 2 treatment groups, adjusting for baseline status using rank analysis of covariance (ANCOVA) {LaVange 2008}.

The number and percentage of subjects in each category based on percentage change from baseline (or open-label baseline) in hip BMD and spine BMD (> 7% decrease, > 5% to \leq 7% decrease, > 3% to \leq 5% decrease, > 1% to \leq 3% decrease, > 0 to \leq 1% decrease, 0 to \leq 1% increase, > 1% to \leq 3% increase, > 3% to \leq 5% increase, > 5% to \leq 7% increase, > 7% increase) will be summarized by treatment group and visit using observed data. Only for the entire study treatment period summary, the distribution difference in these categories between the 2 treatment groups will be compared using the CMH test (row mean scores differ statistic).

Median (Q1, Q3) and mean (95% CIs) of percentage change from baseline to Week 96 in observed hip BMD and spine BMD over time will be plotted by treatment group for subjects in the corresponding Hip and Spine DXA Analysis Sets. This will be repeated using subjects in the Open-Label Hip and Spine DXA Analysis Sets from open-label baseline to Week 96.

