Table 1-9 presents measure of BMD at Week 48. Percentage changes from baseline in hip and spine BMD were the first and second key alpha-controlled safety endpoints in Studies GS-US-320-0108 and GS-US-320-0110. Mean percentage decreases from baseline in BMD at the hip or spine were smaller in the TAF group compared with the TDF group (p < 0.001). A lower percentage of subjects in the TAF group had a > 3% decrease in hip BMD compared with subjects in the TDF group (8.4% TAF; 26.7% TDF). Similarly, a lower percentage of subjects in the TAF group had a > 3% decrease in spine BMD compared with subjects in the TDF group (TAF 19.5%; TDF 38.1%). At Week 48, fewer subjects had ≥ 7% decrease in hip BMD (TAF 0.4%; TDF 2.0%) and ≥ 5% decrease in spine BMD (TAF 6.3%; TDF 20.4%) in the TAF group compared with the TDF group.

Table 1-9. GS-US-320-0108 and GS-US-320-0110: Measures of Bone Mineral Density at Week 48 (Hip DXA Analysis Set and Spine DXA Analysis Set)

	N	TAF 25 mg	N	TDF 300 mg
Hip DXA Analysis Set				
Mean (SD) Percent Change in Hip BMD	807	-0.163 (2.2437)	404	-1.860 (2.4525)
P-Value ^a	< 0.001			
Difference in LSM	1.697 (1.420, 1.974)			
Subjects with > 3% Decrease in Hip BMD, n (%)	807	68 (8.4%)	404	108 (26.7%)
P-Value ^b	< 0.001			
Subjects with > 3% Increase in Hip BMD, n (%)	807	55 (6.8%)	404	8 (2.0%)
P-Value ^b	< 0.001			
Subjects with no Decrease (≥ Zero %Change) in Hip BMD, n (%)	807	383 (47.5%)	404	83 (20.5%)
Spine DXA Analysis Set				
Mean (SD) Percent Change in Spine BMD	814	-0.570 (2.9147)	407	-2.366 (3.2051)
P-Value ^a	< 0.001			
Difference in LSM	1.796 (1.437, 2.155)			
Subjects with > 3% Decrease in Spine BMD, n (%)	814	159 (19.5%)	407	155 (38.1%)
P-Value ^b	< 0.001			
Subjects with > 3% Increase in Spine BMD, n (%)	814	89 (10.9%)	407	11 (2.7%)
P-Value ^b		< 0.	001	
Subjects with no Decrease (≥ Zero %Change) in Spine BMD, n (%)	814	331 (40.7%)	407	89 (21.9%)

DXA = dual-energy x-ray absorptiometry; LSM = least-squares mean

Renal Safety

In the TAF Phase 3 Safety Population in Studies GS-US-320-0108 and GS-US-320-0110 (TAF 25 mg N = 866, TDF 300 mg N = 432; Total N = 1301), no cases of proximal renal tubulopathy (including Fanconi syndrome) or renal failure were reported in either treatment group. No subject in the TAF Phase 3 Safety population experienced a renal SAE or AE resulting in discontinuation of study drugs while on study.

Summary of Renal Laboratory Parameters

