8. STATISTICAL CONSIDERATIONS

8.1. Analysis Objectives and Endpoints

8.1.1. Analysis Objectives

The primary objectives of this study are as follows:

- To evaluate the efficacy of switching to TAF 25 mg QD versus continued TDF 300 mg QD in virologically suppressed subjects with chronic HBV as determined by the proportion of subjects with HBV DNA ≥ 20 IU/mL (as defined by the modified US FDA-defined snapshot algorithm) at Week 48
- To compare the safety and tolerability of switching to TAF 25 mg QD versus continuing TDF 300 mg QD in virologically suppressed subjects with chronic HBV at Week 48

The key secondary objectives of this study are as follows:

- To compare the safety of switching to TAF 25 mg QD versus continued TDF 300 mg QD as determined by the percent change from baseline in hip and spine bone mineral density (BMD) at Week 48
- To compare the safety of switching to TAF 25 mg QD versus continued TDF 300 mg QD as determined by the change from baseline in estimated creatinine clearance by Cockcroft-Gault method (eGFR_{CG}) at Week 48

Other secondary objectives of this study are as follows:

- To evaluate the proportion of subjects with HBV DNA < 20 IU/mL and target detected/not detected (i.e. < LLOD) at Week 48 in subjects switched to TAF 25 mg QD versus continued TDF 300 mg QD
- To compare the safety of switching to TAF 25 mg QD for 96 weeks versus continued TDF 300 mg QD for 48 weeks followed by open-label TAF for 48 weeks as determined by the percent change from baseline in hip and spine bone mineral density (BMD) at Week 96
- To compare the safety of switching to TAF 25 mg QD for 96 weeks versus continued TDF 300 mg QD for 48 weeks followed by open-label TAF for 48 weeks as determined by the change from baseline in estimated creatinine clearance by Cockcroft-Gault method (eGFR_{CG}) at Week 96
- To compare the serological response (loss of HBsAg and seroconversion to anti-HBs, and loss of HBeAg and seroconversion to anti-HBe in HBeAg-positive subjects) of switching to TAF 25 mg QD versus continued TDF 300 mg QD at Week 48

- To compare biochemical response (normal ALT and normalized ALT) of switching to TAF 25 mg QD versus continued TDF 300 mg QD at Week 48
- To compare the change in fibrosis as assessed by FibroTest[®] for switching to TAF 25 mg QD versus continued TDF 300 mg QD at Week 48

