8.1.3. Secondary Endpoint

The secondary efficacy endpoints are:

- The proportion of subjects with HBV DNA ≥ 20 IU/mL (as determined by the modified US FDA-defined snapshot algorithm) at Week 96
- The proportion of subjects with HBV DNA < 20 IU/mL and target detected/not detected (i.e. < LLOD) at Weeks 48 and 96, as determined by the modified US FDA-defined snapshot algorithm
- The proportion of subjects with HBeAg loss and proportion with seroconversion to anti-HBe at Weeks 48 and 96

- The proportion of subjects with HBsAg loss and proportion with seroconversion to anti-HBs at Weeks 48 and 96
- The proportion of subjects with normal ALT and proportion with normalized ALT (by central laboratory and AASLD criteria) at Weeks 48 and 96
- The change from baseline in fibrosis as assessed by FibroTest[®] at Weeks 48 and 96

The key secondary safety endpoints are:

- The percent change from baseline in hip bone mineral density (BMD) at Week 48
- The percent change from baseline in spine bone mineral density (BMD) at Week 48
- The change from baseline in eGFR_{CG} (measured by Cockcroft-Gault method) at Week 48

The secondary safety endpoints are:

- The percent change from baseline in hip bone mineral density (BMD) at Week 96
- The percent change from baseline in spine bone mineral density (BMD) at Week 96
- The change from baseline in eGFR_{CG} (measured by Cockcroft-Gault method) at Week 96

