1.1. Study Objectives

The primary objectives of this study are as follows:

- To evaluate the efficacy of switching to tenofovir alafenamide (TAF) 25 mg once daily (QD) versus continuing tenofovir disoproxil fumarate (TDF) 300 mg QD in virologically suppressed subjects with chronic hepatitis B virus (HBV) as determined by the proportion of subjects with HBV DNA ≥ 20 IU/mL (as defined by the modified United States (US) Food and Drug Administration (FDA) defined snapshot algorithm) at Week 48
- To compare the safety and tolerability of switching to TAF 25 mg QD versus continuing TDF 300 mg QD in virologically suppressed subjects with chronic HBV at Week 48

The key secondary objectives of this study are as follows:

- To compare the safety of switching to TAF 25 mg QD versus continuing TDF 300 mg QD as determined by the percent change from baseline in hip and spine bone mineral density (BMD) at Week 48
- To compare the safety of switching to TAF 25 mg QD versus continuing TDF 300 mg QD as determined by the change from baseline in estimated creatinine clearance by Cockcroft-Gault method (eGFR_{CG}) at Week 48

Other secondary objectives of this study are as follows:

- To evaluate the proportion of subjects with HBV DNA < 20 IU/mL and target detected/not detected (ie, < lower limit of detection [LLOD]) at Week 48 in subjects who switched to TAF 25 mg QD versus those who continued TDF 300 mg QD
- To compare the safety of switching to TAF 25 mg QD for 96 weeks versus continuing TDF 300 mg QD for 48 weeks followed by open-label TAF for 48 weeks as determined by the percent change from baseline in hip and spine BMD at Week 96

- To compare the safety of switching to TAF 25 mg QD for 96 weeks versus continuing TDF 300 mg QD for 48 weeks followed by open-label TAF for 48 weeks as determined by the change from baseline in eGFR_{CG} at Week 96
- To compare the serological response (loss of hepatitis B surface antigen [HBsAg] and seroconversion to antibody against hepatitis B surface antigen [anti-HBs], and loss of hepatitis B e antigen [HBeAg] and seroconversion to antibody against hepatitis B e antigen [anti-HBe] in HBeAg-positive subjects) of switching to TAF 25 mg QD versus continued TDF 300 mg QD at Week 48
- To compare biochemical response (normal alanine aminotransferase [ALT] and normalized ALT) of switching to TAF 25 mg QD versus continued TDF 300 mg QD at Week 48

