FibroTest score will be summarized using descriptive statistics (sample size, mean, SD, median, Q1, Q3, minimum, and maximum) by treatment group for subjects in the FAS. The p-value, differences in change from baseline in FibroTest score between the 2 treatment groups and the associated 95% CI will be constructed using ANOVA models, including treatment group, baseline HBeAg status (HBeAg-positive or HBeAg-negative) and age (< 50 or ≥ 50 years) as fixed effects in the model. A shift table of fibrosis stage from baseline based on the FibroTest score at Week 24, 48, and 96 will be provided. Mean change from baseline in FibroTest score will be plotted with 95% CI over time using observed data from baseline to Week 96. A listing of fibrosis assessment by FibroTest will also be provided.

All the analyses of the secondary efficacy endpoints, using both the M F and the M E approach, and plots described above will be repeated for subjects in the Open-Label FAS from open-label baseline to Week 96. No statistical comparisons will be performed.

For subjects in the TFFU FAS, only HBV DNA, ALT, HBsAg, HBeAg loss/seroconversion, and HBsAg loss/seroconversion endpoints will be summarized by visit in the TFFU phase as described above only using the M E approach. No statistical comparisons will be performed.

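### SAP 7.3.1 plans no between-arm estimate, in percentage points with a 95% CI, of the hip and spine BMD difference at Week 96

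*SAP*

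**What the plan says.** Protocol 8.1.1 makes it an objective to compare 96 weeks of TAF with 48 weeks of TDF followed by 48 weeks of TAF on "percent change from baseline in hip and spine bone mineral density (BMD) at Week 96". SAP 1.1 repeats the objective: "percent change from baseline in hip and spine BMD at Week 96". Protocol 8.1.3 lists the hip measure as a secondary safety endpoint, "The percent change from baseline in hip bone mineral density (BMD) at Week 96", and lists spine in the same way.

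SAP 7.3.1 deals with BMD in four steps:

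- Percent change, the continuous variable: "hip BMD and spine BMD during the entire study treatment period will be summarized by treatment group and visit using descriptive statistics".
- Clinical status (normal, osteopenia, osteoporosis): the arms are compared by rank ANCOVA adjusted for baseline status.
- Percent change cut into ten ordered categories: "the distribution difference in these categories between the 2 treatment groups will be compared using the CMH test (row mean scores differ statistic".
- Plots: "Median (Q1, Q3) and mean (95% CIs) of percentage change from baseline to Week 96 in observed hip BMD and spine BMD over time", drawn by treatment group, so each interval belongs to one arm's mean.

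The protocol promises no more than this for Week 96. Its synopsis says that BMD summaries by original arm continue annually through Week 96 and that secondary continuous endpoints receive an eight-number summary. The treatment-effect ANOVA in Protocol 8.7.1 is for Week 48.

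**The concern.** The objective is a comparison on a continuous scale, yet no planned analysis returns a between-arm difference on that scale. The CMH test gives a p-value on category scores, and the rank ANCOVA gives one on a three-level status.

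The SAP does more for another continuous secondary endpoint at Week 96. In section 6.2.2, "differences in change from baseline in FibroTest score between the 2 treatment groups and the associated 95% CI will be constructed using ANOVA models", with HBeAg status and age as fixed effects. The two earlier Phase 3 studies in CHB, shown in Protocol Table 1-9, also reported an LS-mean BMD difference with its 95% CI.

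By Week 96 both arms are on TAF. The useful result is therefore how many percentage points of BMD still separate an early from a delayed switch, and with what uncertainty. A p-value on categories does not answer that.

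**Working it through.** **1. The plan's own figures.** Inputs from Protocol 8.9: 230 per arm; hip difference 1.81 points, SDs 2.71 and 2.83; spine difference 2.00 points, SDs 3.84 and 4.14; two-sided alpha 0.05.

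- Pooled SD: hip √((2.71² + 2.83²)/2) = 2.771; spine √((3.84² + 4.14²)/2) = 3.993.
- Standard error = SD × √(2/230): hip 0.258, spine 0.372.
- Power from difference/SE − 1.96: hip 7.01 − 1.96 = 5.05, above 99.99%; spine 5.37 − 1.96 = 3.41, about 99.97%.

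The stated figure of more than 99% at Week 48 is reproduced for both sites. The plan states no power or precision for BMD at Week 96.

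**2. Can a reader recover the difference from per-arm summaries?** Table 1-9 allows a test. Hip: 807 and 404 subjects, means −0.163 and −1.860, SDs 2.2437 and 2.4525. The n-weighted pooled SD is 2.315 and the SE is 2.315 × √(1/807 + 1/404) = 0.141. The difference is 1.697 ± 1.962 × 0.141, or 1.420 to 1.974. The same steps for spine (814 and 407; −0.570 and −2.366; 2.9147 and 3.2051) give 1.796, 1.437 to 2.155. Both match the printed values, so an unadjusted difference can be recovered.

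**3. Expected precision at Week 96.** Half-width = t(0.975, 2n − 2) × SD × √(2/n). The documents give no Week 96 SD, so two Week 48 sets are used: the planning SDs, and the CHB SDs from Table 1-9 pooled for equal arms (hip 2.350, spine 3.063). The loss of scans is also an assumption.

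| n per arm | Hip, planning SD | Hip, Table 1-9 SD | Spine, planning SD | Spine, Table 1-9 SD |
|---|---|---|---|---|
| 230 | 0.51 | 0.43 | 0.73 | 0.56 |
| 207 (10% missing) | 0.54 | 0.45 | 0.77 | 0.59 |
| 184 (20% missing) | 0.57 | 0.48 | 0.82 | 0.63 |

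Suppose a quarter of the planned Week 48 difference remained (assumption). At the planning SDs the result would read 0.45 ± 0.51 for hip and 0.50 ± 0.73 for spine. If half remained, it would read 0.91 ± 0.51 and 1.00 ± 0.73.

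**4. Effect of adjustment.** Covariates multiply the half-width by √(1 − R²). The documents give no R². Over an assumed 0.05 to 0.30 the factor runs from 0.975 to 0.837, so at 230 per arm and planning SDs hip goes from 0.51 to between 0.49 and 0.42, and spine from 0.73 to between 0.71 and 0.61.

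**5. Does the categorical test lose power?** Simulation: 10,000 runs, normal data at the planning SDs, 230 per arm, the ten SAP categories scored 1 to 10, two-sided 0.05, holding either the TAF or the TDF mean at its planned value.

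| Share of planned difference remaining (assumption) | Hip: CMH / t-test | Spine: CMH / t-test |
|---|---|---|
| One quarter | 40–42% / 42% | 25–28% / 26–27% |
| One half | 93–94% / 94–95% | 75–77% / 77% |

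The test is nearly as powerful as a t-test. What is missing is the estimate.

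**The case against.** The strongest reply is that the SAP does what the protocol planned, and more. The synopsis promises only summaries for BMD at Week 96, and Protocol 8.1.3 keeps the formally tested key safety endpoints at Week 48. SAP 7.3.1 adds two between-arm tests, so the arms are compared, and no objective names an LS-mean difference. Several other safety measures, including eGFR_CG at Week 96, get a p-value without an interval. FibroTest is an efficacy endpoint. The model behind Table 1-9 contained treatment only, so it is no precedent for adjustment. Nothing in the documents shows that the strata predict BMD change.

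All of that stands, and it limits the point to a better estimate. It does not remove the point. eGFR_CG is at least tested on its own scale, whereas percent change in BMD is neither tested nor estimated on its own. A difference worked out by readers is not a prespecified one.

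A reader might go further and infer that the SAP breaches the protocol, leaves BMD uncompared or threatens the error rate. The documents support none of these. The protocol wording and the two tests answer the first two, and Week 96 BMD lies outside the fallback sequence in Protocol 8.4. A reader might also infer that the Week 48 BMD and eGFR_CG analyses wrongly omit strata and baseline. That cannot be established: Protocol 8.7.1 leaves the details to the SAP, the separate Week 48 SAP cited in SAP 6.1.1 is not among the documents, and SAP 2.2 says the Week 48 analysis has been done.

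**Conclusion.** The point holds as a minor improvement in reporting, not as an error. A stated comparison on a continuous scale has no prespecified between-arm estimate on that scale.

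The estimate would be informative: a half-width of 0.43 to 0.51 points for hip and 0.56 to 0.73 for spine at 230 per arm, against planned Week 48 differences of 1.81 and 2.00. These widths assume that Week 48 SDs carry over to Week 96 and that every subject has a scan. The gap in the text is certain. How much adjustment would narrow the interval is not, because it depends on an R² that the documents do not give.

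**What to change.** In SAP 7.3.1, for the summary covering the entire treatment period, add an ANCOVA of percent change in hip BMD, and another for spine BMD, at Week 96. Include treatment group, age stratum, HBeAg stratum and baseline BMD. Report the LS-mean difference (TAF minus TDF-then-TAF) with its 95% CI, labelled exploratory and outside the alpha-controlled sequence. Keep the CMH and rank ANCOVA tests as planned.

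The cost is one model statement and one table row per site. Baseline BMD and both strata are already collected, and the stratum terms are already used for FibroTest in SAP 6.2.2. SAP section 7 already permits comparisons over the entire treatment period. No visit, sample size or Week 48 conclusion changes.
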